		 step) and stops when the lens is placed on eye. If the lens feels uncomfortable and must be removed, the subject may skip to the lens removal step for that eye. The lens should be inspected for damage and replaced if necessary. If the lens is very uncomfortable needs to be removed immediately, the Investigator or designated staff may do so. The lens should be inspected for damage and replaced if necessary. The Investigator or designated staff will re-insert the lens for the subject. 	
		Removal: Using a stopwatch or a Timer App, observe the subject and record how long it takes them to remove each lens (one at a time). • Total removal time OD • Total removal time OS Total removal time OU Note:	
		 Removal time starts when the subject first attempts to remove the lens (at the approach 	

	Visit 1: Treatment 1 Lens Fitting			
Step	Procedure	Details		
		step) and stops when the lens is successfully removed. • Lenses should be discarded after removal. Note: A slit-lamp examination may be performed at any time during the learning session if the subject's eye(s) seems red or irritated.		
1.19	I&R Learning Session - End	Enter the time when I&R learning session ends. • I&R learning session ends after the subject completes the insertion and removal of both right and left lenses (or when the subject or Investigator stops the learning session). I&R learning session – End Total learning session time OU Note:		
		 The learning session may end prematurely if the subject wishes to stop. Investigator may end the learning session prematurely if the subject's eye(s) seems red or irritated, and a slit-lamp examination may be done. Ample time (approximately 1 hour) should be allowed for the subject to practice and complete insertion and removal tasks. If the subject does not complete the learning session within a reasonable time, a second (and final) training opportunity may be provided on a separate day. The subject may return on the following day and up to day 7. 		
1.20	Completion of I&R Learning Session	Record in EDC whether the subject completed the I&R learning session (insertion and removal of lenses at least once for each eye). If a patient did not complete the Learning Session and will come back for a second training/learning session, a second baseline, including Medical History and Concomitant Medications update, Entrance VA, and Slit lamp biomicroscopy will be captured.		

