1.32	Continuance	For the subject to continue in the study, they must meet all three of the following criteria: • Visual acuity is 20/30 or better OD and OS. • The lens fit is acceptable OD and OS. • Investigator approval.

04-	Visit 1: Treatment 1 Lens Fitting			
Step	Procedure	Details If the Investigator does not approve the dispensing of the first study lens, then the study is terminated for that subject.		
1.33	Dispense	that subject. The lenses will be dispensed for a 6-8 day wearing period. Subjects will be encouraged to wear the study lenses every day, building up the wearing time if necessary. The lenses will be worn in a daily wear, daily disposable modality. Rewetting drops are permitted if needed. The subject should only use the sponsor supplied lens care products. (Section 6.1) Supply the subject a bottle of contact lens solution or saline for rinsing purposes, if necessary. Instruct subjects to return any unworn lenses to the clinical site. Subjects will be scheduled for their 1-week follow-up visit, ensuring that they wear the study lens to the follow-up visit. Note: Dispense the subject enough lenses to last them to their next scheduled visit, plus an extra pair. If the subject requires additional replacement lenses, instruct them to contact the clinical site for replacement. As much as reasonably possible, any damaged lens and packaging should be returned to the clinical site (wet, if possible) and then returned to the Sponsor. If lens damage is present, complete the Product Quality Complaint Form. If the PQC is due to foreign matter in the packaging, to the extent possible, this foreign matter must also be returned. The lens will be stored in labeled vial with saline, and clearly differentiated from the other worn lenses that will be shipped back to the Sponsor.		
1.34	Schedule next visit	The subject may continue to wear their habitual correction (spectacles) when not wearing study contact lenses. Schedule the follow-up visit to occur in 7 ± 1 days (counting the day of this visit as day 0, the subject may return on day 6 through 8). Ensure the subject is instructed to wear the study lenses to the follow-up visit. Remind the subject to bring their spectacle		

VISIT 2

The subjects must present to Visit 2 wearing the study lenses. If the subject wishes to stop wearing contact lenses (discontinue), proceed to the Final evaluation.

		Visit 2: Treatment 1 Follow-Up 1	- 39
Step	Procedure	Details	

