The transmittance characteristics for these lenses are less than 1% in the UVB range of 280 nm to 315 nm and less than 10% in the UVA range of 316 nm to 380 nm for the entire power range.

NOTE: Long-term exposure to UV radiation is one of the risk factors associated with cataracts. Exposure is based on a number of factors such as environmental conditions (altitude, geography, cloud cover) and personal factors (extent and nature of outdoor activities). UV-Blocking contact lenses help provide protection against harmful UV radiation. However, clinical studies have not been done to demonstrate that wearing UV-Blocking contact lenses reduces the risk of developing cataracts or other eye disorders. The Eye Care Professional should be consulted for more information.

INDICATIONS (USES)

ACUVUE OASYS® Brand Contact Lenses 1-Day with HydraLuxe™
Technology are indicated for daily disposable wear for the optical correction of refractive ametropia (myopia and hyperopia) in phakic or aphakic persons with non-diseased eyes who may have 1.00D or less of astigmatism.

ACUVUE OASYS® Brand Contact Lenses 1-Day with HydraLuxe™ Technology for ASTIGMATISM are indicated for daily disposable wear for the optical correction of refractive ametropia (myopia and hyperopia) in phakic or aphakic persons with non-diseased eyes who may have 0.50D to 3.00D of astigmatism.

These lenses contain a UV Blocker to help protect against transmission of harmful UV radiation to the cornea and into the eye.

CONTRAINDICATIONS (REASONS NOT TO USE)

DO NOT USE these contact lenses when any of the following conditions exist:

- Acute or subacute inflammation or infection of the anterior chamber of the eye.
- Any eye disease, injury or abnormality that affects the cornea, conjunctiva, or eyelids.
- Severe insufficiency of lacrimal secretion (dry eye).

- Corneal hypoesthesia (reduced corneal sensitivity).
- Any systemic disease that may affect the eye or be exaggerated by wearing contact lenses.
- Allergic reactions of ocular surfaces or adnexa that may be induced or exaggerated by wearing contact lenses or use of contact lens solutions.
- Ocular irritation due to allergic reactions which may be caused by use of contact lens solutions (i.e., rewetting drops) that contain chemicals or preservatives (such as mercury, Thimerosal, etc.) to which some people may develop an allergic response.
- Any active corneal infection (bacterial, fungal, protozoal, or viral).
- If eyes become red or irritated.

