- The potential impact of these factors on the patient's ocular health should be carefully weighed against the patient's need for refractive correction; therefore, the continuing ocular health of the patient and lens performance on the eye should be carefully monitored by the prescribing Eye Care Professional.
- Patients who wear these lenses to correct presbyopia using monovision may not achieve the best corrected visual acuity for either far or near vision. Visual requirements vary with the individual and should be considered when selecting the most appropriate type of lens for each patient.
- Fluorescein, a yellow dye, should not be used while the lenses are
 on the eyes. The lenses absorb this dye and become discolored.
 Whenever fluorescein is used in eyes, the eyes should be flushed
 with a sterile saline solution that is recommended for in-eye use.
- Eye Care Professionals should instruct the patient to remove the lenses immediately if the eyes become red or irritated.

Eye Care Professionals should carefully instruct patients about the following care regimen and safety precautions.

Handling Precautions:

- Before leaving the Eye Care Professional's office, the patient should be able to promptly remove the lenses or should have someone else available who can remove the lenses for him or her.
- DO NOT use if the sterile blister package is opened or damaged.
- Always wash and rinse hands before handling lenses. Do not get cosmetics, lotions, soaps, creams, deodorants, or sprays in the eyes or on the lenses. It is best to put on lenses before putting on makeup. Water-based cosmetics are less likely to damage lenses than oil-based products.
- DO NOT touch contact lenses with the fingers or hands if the hands are not free of foreign materials, as microscopic scratches of the lenses may occur, causing distorted vision and/or injury to the eye.
- Carefully follow the handling, insertion, removal, and wearing instructions in the "Patient Instruction Guide" for the prescribed

wearing schedule and those prescribed by the Eye Care Professional.

- Always handle lenses carefully and avoid dropping them.
- Never use tweezers or other tools to remove lenses from the lens container unless specifically indicated for that use. Slide the lens up the side of the bowl until it is free of the container.
- Do not touch the lens with fingernails.

Lens Wearing Precautions:

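### Step 1.18 has a lens removed for marked discomfort put back without requiring that the discomfort has stopped or that anyone looks at the eye, which is looser than the package insert

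*Combined protocol and SAP*

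**What the plan says.** Section 7.2, Visit 1, step 1.18 describes the first session in which subjects insert and remove lenses themselves, supported by the Investigator or designated staff. If a lens is so uncomfortable that it has to come out at once, either of them may remove it. The instruction continues: "The lens should be inspected for damage and replaced if necessary. The Investigator or designated staff will re-insert the lens for the subject".

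A note at the end of the step makes an eye examination optional: "A slit-lamp examination may be performed at any time during the learning session if the subject's eye(s) seems red or irritated". Step 1.19 lets the Investigator stop the session early for a red or irritated eye, again with an optional slit-lamp examination. A subject who does not finish may be offered one further session: "The subject may return on the following day and up to day 7". For that subject step 1.20 applies: "If a patient did not complete the Learning Session and will come back for a second training/learning session, a second baseline" is recorded, and it includes slit-lamp biomicroscopy.

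The package insert is reproduced in Appendix C. Its contraindications open with "DO NOT USE these contact lenses when any of the following conditions exist", and the list ends with "If eyes become red or irritated". Under Adverse Reactions, a wearer with a problem is to take the lens out. If the problem stops, that lens is thrown away and a fresh one used. If the problem continues with the new lens, that lens comes out too and the eye care professional is contacted.

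**The concern.** Marked discomfort on first insertion can come from the lens or from the eye. Step 1.18 deals with the first possibility only. If the lens looks sound, the written sequence leads back to insertion whatever the state of the eye.

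The subjects have never handled a lens, and some are 13 to 17 years old. First handling is a foreseeable moment for a corneal abrasion, and the session may be run by designated staff. Section 13.1 counts a corneal abrasion of Grade 3 or higher as a Significant Adverse Event, and the 24-hour reporting limit in section 13.4 runs from discovery, so it helps if someone looks. The bare eye is also easiest to check before a lens goes back on. The insert says "Fluorescein, a yellow dye, should not be used while the lenses are" on the eyes, so checking for staining later means taking the lens out again.

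**Working it through.** No arithmetic applies. The check is to set step 1.18 beside the insert and then see whether any other step supplies what is missing.

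| Question | Step 1.18 | Package insert (Appendix C) |
|---|---|---|
| What happens to the removed lens? | Checked, and exchanged only where needed | Thrown away |
| When may a lens go back on? | No condition stated | Once the discomfort has stopped |
| What if the eye is red or irritated? | Slit-lamp examination optional; no bar on re-insertion stated | Listed as a reason not to use the lens |
| Who must look at the eye? | Nobody is named | Eye care professional contacted if the problem continues with the new lens |

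1. *The lens.* Within step 1.18, a separate note on the timed removal says that lenses are discarded once removed. The discomfort instruction allows the same lens to go back if undamaged. The two do not quite agree, and the note matches the insert.

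2. *The condition for re-insertion.* Nothing in step 1.18 or 1.19 requires a wait or a question about discomfort before the lens goes back. The power in step 1.19 to end the session is discretionary.

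3. *Later steps.* After the session come a new pair (1.22), a slit-lamp check described as being for lens damage (1.23, cut short in the available text), settling (1.24), an open-ended symptom question (1.27), fit (1.28), acuity (1.31) and the continuance decision (1.32), which needs acuity, fit and Investigator approval. These protect the subject before dispensing. All of them come after the re-insertion in question, and none is a condition on it.

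4. *Cross-reference.* Sections 1.4 and 1.5 send the reader to Appendix C for risk and product information. Step 1.18 does not mention it, so staff following the step would not meet the insert's rule there.

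Step 1.18 is therefore looser than the insert on the lens and on when a lens may go back, and it states no bar for a red or irritated eye.

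**The case against.** The strongest reply is that silence is not an instruction. The re-insertion sentence may be meant only to say who puts the lens back. The same step permits a slit-lamp examination at any time in the session, and staff are present throughout. A reader might infer that the protocol tells staff to replace the lens without looking. It does not; it only fails to require a look. That part of the reply stands.

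Existing cover also counts. The symptom question, fit, acuity and Investigator approval all come before dispensing. Section 7.3 provides for slit-lamp findings at unscheduled visits, and the insert says patients should be told to remove lenses and promptly seek care for discomfort or redness. Appendix E, the training guide that step 1.16 points to, cannot be read in the available text, and the Patient Instruction Guide is supplied separately. Either may deal with a painful lens.

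A reader might go further and ask for a graded slit-lamp examination, or a ban on lenses until all redness clears, before any subject is dispensed. The documents do not support that. The insert's fitting procedure calls for a slit-lamp check of centration and movement and then dispensing, with no graded bare-eye examination after training. Step 1.13 stops a subject at Grade 3 or higher, not for mild redness. Section 4.2 chose a design close to ordinary fitting, which is consistent with leaving the examination to the Investigator. Deferral would also leave open which timed session counts as the initial fitting.

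Nor does step 1.32 show that a new deferral route is needed for subjects who finish the session. It does say "If the Investigator does not approve the dispensing of the first study lens, then the study is terminated for that subject". But the Investigator can stop the session earlier under step 1.19, and sections 4.3 and 8.2 allow discontinued subjects to be replaced.

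What the reply does not answer is the comparison with the insert. The insert makes a fresh lens conditional on the discomfort stopping; step 1.18 states no condition.

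**Conclusion.** The point holds as a minor one worth acting on. For a lens removed because of marked discomfort, step 1.18 is looser than the product's own insert, and nothing else in the readable text closes the gap before the lens goes back.

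Its size cannot be stated. The documents give no rate for lenses removed in the learning session, for irritated eyes, or for abrasions, so any count of missed findings would be invented. The point concerns participant safety only. A reader might infer bias in the primary endpoint, but that endpoint is the percentage of eyes with lens-related Grade 3 or 4 findings after about two weeks of wear, and this step does not directly affect it.

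The conclusion rests on two assumptions: that the unreadable Appendix E and the separate Patient Instruction Guide do not already set the rule, and that the insert's advice to wearers is a fair standard for a supervised session. The second is reasonable, since the Investigator is available to look at the eye.

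**What to change.** In step 1.18, replace the re-insertion sentence with:

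> After removal for marked discomfort, the lens is discarded and a new lens is inserted, by the Investigator or designated staff, only once the discomfort has stopped and the Investigator has looked at the eye; otherwise the session is ended under step 1.19.

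The instruction just before it, on inspecting and exchanging the lens, should be trimmed to match. Whether to use the slit lamp stays with the Investigator. Steps 1.20 and 1.32 need no change. A subject whose session is stopped can use the existing second session, with its repeat baseline.

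The cost is a few minutes of Investigator time when a lens is removed for marked discomfort, one extra lens, and an occasional session moved to another day. The pause should fall outside the insertion and removal times, which run from first attempt to lens on or lens off. It would lengthen the total session time recorded at step 1.19, which is not a listed endpoint. If Appendix E already contains this rule, a cross-reference from step 1.18 would be enough.

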1.13	Slit Lamp Biomicroscopy	FDA Slit Lamp Classification Scale will be used to grade the findings. If any of these slit lamp findings are grade 3 or higher, the subject may not continue at this time, but may return up to one additional time to determine eligibility. If discontinued a final examination must be completed. If the clearance of the fluorescein needs to be expedited, preservative-free rewetting drops or saline may be instilled.		
1.14	Eligibility after Baseline	All responses to Inclusion Criteria questions must be answered "yes" and all responses to Exclusion Criteria questions must be answered "no" for the subject to be considered eligible. If the subject is deemed to be ineligible after baseline, proceed to Final Evaluation and complete Subject Disposition. Refraction and Biomicroscopy forms do not need to be completed as part of Final Evaluation.		

	Visit 1: Treatment 1 Lens Fitting		
Step	Procedure	Details	
1.15	Lens Selection	Select the contact lens power based on vertex corrected spherical equivalent of the subjects spherocylindrical refraction.	

		Visit 1: Treatment 1 Lens Fitting	13
Step	Procedure	Details	
1.16	Insertion & Removal training	Study investigator or designated staff will train the subject on insertion and removal of lenses, demonstrating how to retrieve the lenses from the package, position the lens on the finger, secure the eyelids, and how to insert and remove the lenses.	Appendix E
1.17	I&R Learning Session - Start	Enter the time when I&R learning session begins.	
1.18	Learning Session: Lens Insertion & Removal	While being timed, the subject will insert and remove the study lenses on their own, one at a time. The Investigator or designated staff will support the subject throughout the learning session. Insertion: Using a stopwatch or a Timer App, record how long it takes the subject to insert each lens (one at a time). • Enter total insertion time OD • Enter total insertion time OS Total insertion time OU Note: • Insertion time starts when the subject first attempts to insert the lens (at the approach	

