2.12	Slit Lamp Biomicroscopy	FDA Slit Lamp Classification Scale will be used to grade the findings. If the subject has a Grade 3 slit lamp finding, it will be recorded as an Adverse Event and the subject will be monitored as per the guidelines given in section 13. If the clearance of the fluorescein needs to be expedited, preservative-free rewetting drops may be	
2.13	Lens Insertion (timed)	instilled. While being timed, the subject will re-insert the study lenses on their own, one at a time. Insertion: Using a stopwatch or a Timer App, observe the subject	
		and record how long it takes for them to insert each lens (one at a time). • Enter total insertion time OD • Enter total insertion time OS Total insertion time OU Note: • Insertion time starts when the subject first attempts to insert the lens (at the approach step) and stops when the lens is placed on eye. • You may ask the subject to let you know when the lens is in.	
2.14	Subjective Best Sphere Over Refraction (if applicable)	An over-refraction may be performed at the Investigators discretion. Perform subjective best sphere refraction over the study lenses with a phoropter, trial lenses, or flipper bars OD and OS. Record the best corrected distance visual acuity to the nearest letter (OD and OS).	
2.15	Lens Power Modification	Note: The subject may continue in the study if the over-refraction is Plano, at the Investigators discretion. Adjust the lens power if the subject's best sphere over-	
	(if applicable)	refraction is not Plano. Up to two power modifications are allowed.	
2.16	Subject Reported Ocular Symptoms (if applicable)	Subjects will respond to a verbal open-ended symptoms questionnaire.	
2.17	Exit VA	Record the subject's distance visual acuity, OD and OS, to the nearest letter.	

		Visit 2: Treatment 1 Follow-Up 1
Step	Procedure	Details
2.18	Continuance	For the subject to continue in the study, they must meet all three of the following criteria: • Visual acuity is 20/30 or better OD and OS. • The lens fit is acceptable OD and OS. • Investigator approval. If the Investigator does not approve the dispensing of the first study lens, then the study is terminated for that subject.

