13. ADVERSE EVENTS

13.1. Definitions and Classifications

Adverse Event (AE) – An AE is "any untoward medical occurrence, unintended disease or injury, or untoward clinical signs (including abnormal laboratory findings) in subjects, users or other persons, whether or not related to the investigational medical device and whether anticipated or unanticipated."

NOTE: This definition includes events related to the investigational medical device or the comparator, and to the procedures involved. For users or other persons, this definition is restricted to events related to investigational medical devices.¹

An AE includes any condition (including a pre-existing condition) that:

- 1. Was not present prior to the study but appeared or reappeared following initiation of the study.
- 2. Was present prior to the study but worsened during the study. This would include any condition resulting from concomitant illnesses, reactions to concomitant medications, or progression of disease states.

NOTE: Pregnancy must be documented as an adverse event and must be reported to the clinical monitor and to the Sponsor immediately upon learning of the event.

Serious Adverse Event (SAE) – An SAE is any adverse event that led to any of the following:

- Death
- Serious deterioration in the health of the subject that resulted in any of the following:
- Life-threatening illness or injury
- Permanent or persistent impairment of a body structure or a body function
- Hospitalization or prolongation of patient hospitalization
- Medical or surgical intervention to prevent life-threatening illness or injury or permanent impairment to a body structure or a body function.
- Chronic disease
- Fetal distress, fetal death or a congenital physical or mental impairment of birth defect.

Diagnoses and conditions that are considered Ocular Serious Adverse Events include, but not limited to:

- Microbial Keratitis (MK)
- Iritis (including cells in the anterior chamber)
- Permanent decrease in best spectacle corrected visual acuity equivalent to 2 acuity lines or greater
- Central Corneal Opacity
- Central Corneal Neovascularization
- Uveitis
- Endophthalmitis
- Hypopyon
- Hyphemia
- Penetration of Bowman's Membrane
- Persistent Epithelial Defect
- Limbal cell Damage leading to Conjunctivalization

Significant Adverse Events – are defined as events that are symptomatic and warrant discontinuation (temporary or permanent) of the contact lens wear.

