Diagnoses and conditions that are considered Ocular Significant Adverse Events include, but not limited to the following:

- Contact Lens Induced Peripheral Ulcer (CLPU)
- Significant Infiltrative Events (SIE)
- Superior Epithelial Arcuate Lesions (SEALs)
- Contact Lens-induced Acute Red Eye (CLARE)
- Any Temporary Loss of > 2 Lines of BCVA
- Other grade 3 or higher corneal findings, such as abrasions or edema
- Non-contact lens related corneal events e.g. Epidemic Keratoconjunctivitis (EKC)
- Asymptomatic Corneal Scar
- Any corneal event which necessitates temporary lens discontinuation > 2 weeks

Non-Significant Adverse Events – are defined as those events that are usually asymptomatic and usually do not warrant discontinuation of contact lens wear but may cause a reduction in wear time. However, the Investigator may choose to prescribe treatment as a precautionary measure.

Diagnoses and conditions that are considered Ocular Non-Significant Adverse Events include, but not limited to the following:

- Non-significant Infiltrative Event (NSIE)
- Contact Lens Papillary Conjunctivitis (CLPC)
- Superficial Punctate Keratitis (SPK)
- Conjunctivitis: Bacterial, Viral, Allergic
- Blepharitis
- Meibomianitis
- Contact Dermatitis
- Localized Allergic Reactions
- Any corneal event not explicitly defined as serious or significant adverse event, which necessitates temporary lens discontinuation < 2 weeks

Adverse Device Effect (ADE) – An ADE is an "adverse event related to the use of an investigational medical device."

NOTE 1: This definition includes adverse events resulting from insufficient or inadequate instructions for use, deployment, implantation, installation, or operation, or any malfunction of the investigational medical device.

NOTE 2: This definition includes any event resulting from use error or from intentional misuse of the investigational medical device.¹

Unanticipated Adverse Device Effect (UADE) – A UADE is any serious adverse effect on health or safety or any life-threatening problem or death caused by, or associated with, the test article, if that effect, problem, or death was not previously identified in nature, severity, or degree of incidence in the investigational plan, Investigator's Brochure or protocol, or any other unanticipated serious problem associated with the test article that relates to the rights, safety and welfare of subjects.

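### Visit 2 goes from slit-lamp grading straight to timed lens re-insertion with no rule for an eye just graded 3 or 4, and its fluorescein clearance wording differs from the package insert

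*Combined protocol and SAP*

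**What the plan says.** Section 7.2 sets out Visit 2 as numbered steps. Timed removal (2.11) is followed by slit-lamp biomicroscopy (2.12). On grade, 2.12 states: "If the subject has a Grade 3 slit lamp finding, it will be recorded as an Adverse Event", and adds that "the subject will be monitored as per the guidelines given in section 13". On the dye it states: "If the clearance of the fluorescein needs to be expedited, preservative-free rewetting drops may be" instilled. Step 2.13 then directs: "While being timed, the subject will re-insert the study lenses on their own, one at a time". No condition is attached. An optional over-refraction, any power change, a symptom question and exit acuity come next. The continuance check is step 2.18, with three criteria: acuity of 20/30 or better in each eye, acceptable fit in each eye, and investigator approval. The flowchart in the synopsis (Figure 1) shows the same order of removal, slit lamp and insertion.

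Other parts of the document bear on the same moment:

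- Section 8.2 lists grounds for withdrawal, including significant adverse events that require lens wear to stop. For a discontinued subject, the first task it gives the investigator is to complete the visit in progress.
- Section 13.1 says Significant Adverse Events "are defined as events that are symptomatic and warrant discontinuation (temporary or permanent) of the contact lens wear". Its list of ocular examples includes "Other grade 3 or higher corneal findings, such as abrasions or edema".
- Appendix C (package insert) lists, among conditions in which the lenses must not be used, abnormality of the cornea, conjunctiva or eyelids, and eyes that become red or irritated.
- Appendix C also says: "Whenever fluorescein is used in eyes, the eyes should be flushed" with sterile saline suitable for the eye. It explains that the lenses take up the dye and discolour.
- Sections 2.2 and 14.5 define the primary endpoint on Grade 3 or 4 findings.

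**The concern.** A site that follows the Visit 2 steps exactly would have a new wearer put a lens back on an eye whose Grade 3 or 4 finding has just been recorded. For some of those findings, other parts of the same protocol indicate that lens wear should stop or that the lens is contraindicated. Sites could reasonably act in different ways, and an investigator who skips 2.13 has no step that says so.

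The first stake is subject safety. The second is the Visit 2 data. The 1-week insertion time, any over-refraction and the exit acuity are all taken after 2.12. They may therefore come from an affected eye, or with a lens that has absorbed dye. Exit acuity (2.17) immediately precedes the 20/30 criterion in 2.18. If re-insertion is omitted, the insertion time is simply missing: section 14.9 counts missing values without imputing them, and no code is planned to show that a slit-lamp finding was the cause.

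**Working it through.** The main point concerns order and wording, so the check is a comparison of passages. The plan gives no figure to reproduce: section 14.2 states no power calculation and says no prior data were available.

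**1. Is there a branch between grading and re-insertion?** No. Step 2.12 leads to a record and to monitoring, and 2.13 is unconditional. The first check naming investigator approval is 2.18, after the lens is back on the eye. Its other two criteria are acuity and fit, not slit-lamp grade.

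**2. Does another section supply the branch?** Not clearly.
- Section 13.2 allows temporary or permanent discontinuation as an action taken, and section 13.3 leaves continuation in the study to the investigator's judgment. Neither addresses a step within the visit.
- Section 8.2 can end participation, yet has the current visit completed. Read literally, that includes 2.13.
- Section 10 lets an investigator depart from the protocol to remove an immediate hazard, with notice to the sponsor within 24 hours. That permits skipping 2.13, but as a deviation.

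**3. Is the problem specific to Visit 2?** Yes, for re-insertion. At Visit 1 the learning session may be stopped if the eyes look red or irritated (1.19). At Visit 3 the order is insertion (3.12), removal and discard (3.13), then slit lamp (3.14), so no lens follows grading.

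**4. Which findings conflict with another passage?**
- Section 13.1: corneal findings of Grade 3 or higher that meet its definition, that is, symptomatic and warranting discontinuation of wear.
- Appendix C contraindications: these extend to conjunctiva, lids and red or irritated eyes, but only where the finding meets them.

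**5. Fluorescein clearance.**
- Step 1.13 (before insertion at 1.18): optional; rewetting drops or saline.
- Step 2.12 (before insertion at 2.13): optional; rewetting drops only.
- Appendix C: a flush with sterile saline whenever the dye is used, worded as should.

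Eyes potentially affected at a visit: 40 subjects x 2 eyes = 80. This is an upper figure. It assumes every enrolled subject reaches the step and receives fluorescein. The roughly 30 expected completers give 30 x 2 = 60.

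**6. How many Grade 3 or 4 eyes at Visit 2?** The documents give no rate. As an illustration only, under an assumed 1% to 5% of eyes: 60 x 0.01 = 0.6 and 80 x 0.05 = 4.

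**7. Grade wording.** Steps 2.12 and 3.14 name Grade 3 alone. Section 2.2 uses Grade 3 or 4 and Grade 3 or higher, and step 1.13 uses Grade 3 or higher.

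**The case against.** The strongest reply is that safeguards exist and no competent investigator would put a lens on a visibly injured eye. Step 2.12 sends the subject to section 13, where events are classified with the medical monitor. Section 8.2 allows withdrawal on the investigator's safety judgment, and Appendix C, with its contraindications, is part of the protocol. This stands to the extent that the defect is unclear sequencing, not an absence of safeguards. A reader might infer that an adverse event record is the only consequence stated in 2.12. The monitoring clause in the same sentence shows otherwise. What remains is that none of these routes says whether 2.13 applies, and 8.2 points towards finishing the visit.

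A reader might also infer that step 1.13 is contradicted, since there "If any of these slit lamp findings are grade 3 or higher, the subject may not continue at this time". The documents do not support that. Step 1.13 is a baseline eligibility gate before any lens wear, and its own rinse is optional. It shows the same grade handled differently at another stage, nothing more.

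The measurement harm is modest. Insertion time is exploratory and descriptive, the over-refraction is optional, and Table 5 treats an unrecorded time as a minor deviation. The Grade 3 wording is largely editorial, because a Grade 4 finding would still fall under the general adverse event definition. Finally, the text of the Biomicroscopy Scale in Appendix D is not visible, so the clearance discrepancy is shown only for the procedure steps.

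**Conclusion.** The point holds as a reconciliation issue that should be fixed. As written, 2.13 applies to every eye graded 3 or 4 at Visit 2. It conflicts with section 13.1 for qualifying corneal findings and with Appendix C where its contraindications are met. It is not shown to conflict for every Grade 3 or 4 finding: a lid or conjunctival finding is outside the corneal entry in 13.1. The number of such eyes is unknown, and the 0.6 to 4 shown above rests wholly on an assumed rate.

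The clearance discrepancy needs no assumed rate. It reaches up to 80 eyes at each of Visits 1 and 2, provided fluorescein is used in all of them.

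A reader might take the Visit 2 eyes to be the numerator of the primary endpoint. Section 2.2 does not support this: findings are assessed at all visits, but the endpoint is set at about 2 weeks, and the scheduled grading at that time is step 3.14. The point therefore bears on safety at Visit 2 and on exploratory 1-week data, not on the primary percentage as defined. No view is taken on which clinical rule is right.

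**What to change.** - Reconcile steps 2.12, 2.13 and 2.18 with sections 8.2 and 13.1 and with Appendix C, so that the protocol gives one consistent answer on whether timed re-insertion applies after a Grade 3 or 4 finding. The content of that answer is for the sponsor and its medical monitor.
- Reconcile the fluorescein clearance wording in 1.13 and 2.12 with Appendix C.
- Align the grade named in 2.12 and 3.14 with the endpoint's Grade 3 or 4.
- Add an eCRF reason code for an insertion time not obtained because of a slit-lamp finding, so that it can be told apart from other missing values.

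The cost is a few wording changes and one reason code. The possible loss is the exploratory 1-week insertion time in a few subjects, if the reconciled text means that re-insertion is not done.
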